5.2.2. Patient Disposition

A listing of the primary reason for patient discontinuation will be presented for All Randomized patients. Summary analyses will be conducted for the All Randomized and FAS populations. Frequency counts and percentages will be presented for each treatment group and compared across treatment groups using Fisher's Exact Test or Pearson's Chi-square test.

A listing and summary analyses will also be provided for the discontinuation of study drug for the FAS population.

5.2.3. Patient Characteristics

Demographic and baseline characteristics will be summarized by treatment group for all randomized patients, the FAS and PP populations. For continuous measures, summary statistics will include sample size, mean, median, maximum, minimum, and standard deviations (SDs). The treatment groups will be compared using a 2-sample *t*-test. For categorical measures, summary statistics will include sample size, frequency, and percentage. Analysis will use Fisher's Exact test or Pearson's Chi-square test.

5.2.4. Concomitant Therapy

Concomitant medications, including previous therapies for diabetes, will be summarized by different categories and treatment group using the FAS population. All concomitant therapies that originally mapped using the WHODRUG dictionary in the Clintrial database will be further classified using Anatomical Therapeutic Chemical (ATC) level 2 codes for reporting purpose. Analyses will use test Fisher's Exact Test or Pearson's Chi-square test.

5.2.5. Treatment Compliance

No specific study data will be collected for analysis of treatment compliance.

5.2.6. Protocol Violations

A comprehensive listing of patients with important protocol deviations (IPD) or protocol violations that could potentially impact data interpretation, data integrity and patient safety across the I4L-GH-ABES study will be provided. A summary of IPD by treatment group and overall will also be provided.

Important protocol deviations will be identified from the clinical database and from site monitoring. Categories of IPDs will be documented in the “ABES trial issue management plan” that will contain detailed criteria used to identify IPDs. Detailed programming specifications for IPDs (ADaM PD dataset specification) will be stored in CLUWE prior to database lock.

5.2.7. Primary Efficacy Outcome and Methodology

The primary efficacy outcome will be the change in HbA1c level from baseline to 24 weeks. The primary analysis will be a likelihood-based, MMRM approach, treating the data as missing at random (MAR) for the FAS population. The MMRM model will evaluate the change from baseline to each postbaseline visit in HbA1c level as the dependent variable with treatment (LY2963016, Lantus®), pre-study treatment (Lantus®-bolus, other basal-bolus, premixed insulin), and pre-study metformin or acarbose usage (metformin only, acarbose only, or neither), visit, and interaction between visit and treatment as fixed effects; the baseline value of HbA1c as a covariate; and a random effect for patient. The MMRM model will be carried out using the observed margins (OM) option in SAS MIXED procedure. The standard least square means (LSMeans) have equal coefficients across classification effects; however, the OM option changes these coefficients to be proportional to the number of patients used to calculate the classification means. This will provide LSMean estimates that are more representative of the patient population recruited in this study.

The primary treatment comparison is to compare LY2963016 versus Lantus® at the NIM of +0.4%. If the upper limit of the 95% CI on the change from baseline to 24-week endpoint HbA1c for LY2963016 versus Lantus® is below +0.4%, then LY2963016 will be declared noninferior to Lantus®. The LSMean and standard error derived from the MMRM model for each treatment will be used to test noninferiority. Type III sums of squares will be used to make the treatment comparisons.

- If the +0.4% NIM is met, a key secondary treatment comparison will be conducted to show noninferiority of Lantus® to LY2963016. This will be done by comparing Lantus® versus LY2963016 at the NIM of -0.4%. If the lower limit of the 95% CI on the change in HbA1c from baseline to the 24-week endpoint for LY2963016 versus Lantus® is above -0.4%, then Lantus® will be declared noninferior to LY2963016. The LSMean and standard error derived from the MMRM model for each treatment will be used to test noninferiority. This gate-keeping procedure controls the family-wise Type 1 error rate at a 1-sided 0.025 level.

- If LY2963016 is declared noninferior to Lantus® in the primary treatment comparison, and Lantus® is declared noninferior to LY2963016 in this secondary treatment comparison, then LY2963016 will be considered to have equivalent efficacy as Lantus®.

A first secondary analysis of the primary efficacy outcome will use the same MMRM model described above with the PP patient population. Significance tests will be based on LSMeans using the Type III sum of squares, and testing for noninferiority will occur as described above.

A second secondary analysis of the primary efficacy outcome will use an ANCOVA model with FAS population. The ANCOVA model will include treatment, pre-study treatment (Lantus®-bolus, other basal-bolus, premixed insulin), and pre-study metformin or acarbose usage (metformin only, acarbose only, or neither) as fixed effects and the baseline value of HbA1c as a covariate. The ANCOVA model will be carried out using the OM option in SAS GLM procedure. If the 24-week HbA1c value is missing, the last postbaseline value will be carried forward and used in the analysis. This creates the 24-week endpoint value for HbA1c using the LOCF methodology. If there are no HbA1c data after the date of randomization, the endpoint will be considered missing and the patient will not be included in the analysis.

The analyses of the primary efficacy outcome will only be conducted for patients with both nonmissing baseline value and at least 1 nonmissing postbaseline value.

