12.2.10. Subgroup Analyses

The consistency of the treatment effect will be assessed in the following subgroups in the FAS if there are a sufficient number of patients in each treatment by subgroup:

- entry HbA1c levels (<7%, ≥7%)
- entry HbA1c levels (<8.5%, ≥8.5%)
- prestudy treatment (Lantus®-bolus, other basal-bolus, premixed insulin)
- entry BMI (<30, ≥30)
- entry age (<65, ≥65)
- Prestudy metformin or acarbose use (metformin only, acarbose only or neither)
- Renal function, as estimated by estimated glomerular filtration rate (EGFR). The following EGFR categories will be used:
 - normal or increased GFR: EGFR (≥90 mL/min/1.73 m²)
 - mild reduction in GFR: EGFR (60 to 89 mL/min/1.73 m²)
 - Moderate reduction in GFR: EGFR (30 to 59 mL/min/1.73 m²)
 - Severe reduction in GFR: EGFR (15 to 29 mL/min/1.73 m²)
 - Kidney failure: EGFR (<15 mL/min/1.73 m²).

The change in HbA1c from baseline to 24-week endpoint will be analyzed using MMRM with treatment, visit, prestudy treatment, prestudy metformin or acarbose usage, subgroup, subgroup-by-treatment interaction, subgroup-by-visit interaction, treatment-by-visit interaction, and treatment-by-visit-by-subgroup interaction as fixed-effects, the baseline value of HbA1c as a covariate, and a random effect for patient for the FAS. If the subgroup is one of the stratification variables, then the subgroup will only be included once in the model. A significant treatment-by-subgroup interaction ($p < .05$) may be indicative of a differential treatment effect across levels of the subgroup, necessitating further exploration of the nature of the interaction.

Other subgroup analyses may be performed if deemed appropriate as exploratory analyses.

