5.1. Determination of Sample Size

5.1.1. Sample Size Section from the Protocol

Based on the primary objective, to show noninferiority of LY2963016 to Lantus® at the 0.40% noninferiority margin (NIM), 109 completers per arm (218 total) are needed at 24 weeks. This calculation assumes no treatment difference in HbA1c between LY2963016 and Lantus®, a common standard deviation (SD) of 1.05% for change from baseline in HbA1c, a two-sided significance level of 0.05, and over 80% power. Assuming a 15% dropout rate at 24 weeks, the required number of randomized patients is 129 per arm (258 total). This sample size is noted as the minimum sample size required in the study.

Blinded sample-size reestimation (bSSR) may be performed when approximately 40% of the subjects have been enrolled in the study and finished 24-weeks of treatment, or about 6 months prior to the completion of enrollment, depending on which occur first by team assessment. This reestimation will use a statistical model to estimate the variability in the change in HbA1c from baseline to 24 weeks using all available patient HbA1c values at the time of data cutoff. The estimate of variability will then be used to recalculate the sample size that would be needed to have 80% power for a NIM of 0.4%, assuming no difference between treatments. The sample size from the study is constrained between a predefined minimum sample size of 258, and a maximum sample size of 400 patients. If the recalculated sample size is smaller than minimum sample size planned, the study will enroll to the minimum sample size. If the recalculated sample size is larger than the planned minimum sample size, the team will make a decision whether to increase sample size to the reestimated sample size, bounded by the predefined maximum, or accept the consequent reduction in power.

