5.2.8. Secondary Efficacy Outcomes and Methodology

The continuous secondary efficacy outcomes include:

- actual and change in HbA1c from baseline to 6, 12, and 18 weeks or LOCF
- 7-point SMBG measurements and change from baseline to each visit (expressed as plasma-equivalent glucose values), as listed in the Study Schedule (see ABES Study Protocol Attachment 1)
 - premeal for each meal
 - postmeal for breakfast and lunch
 - bedtime
 - 3 am
- summaries of 7-point SMBG (actual and change from baseline)
 - daily mean BG level (average across all 7 time points)
 - daily mean premeal BG level (before breakfast, lunch, dinner)
 - daily mean postprandial BG level (breakfast, lunch and bedtime)
 - bedtime to 3 AM excursion
- inpatient variability as measured by the SD of the 7-point SMBG.

- actual and change from baseline total insulin, basal insulin, and mealtime insulin lispro doses in U/day and U/kg/day
- actual and change from baseline in weight and BMI
- patient-reported outcomes as reflected in responses to ITSQ.

The analysis of the continuous secondary efficacy variables will be performed using the same MMRM model with treatment (LY2963016, Lantus®), pre-study treatment (Lantus®-bolus, other basal-bolus, premixed insulin), and pre-study metformin or acarbose usage (metformin only, acarbose only, or neither), visit, and interaction between visit and treatment as fixed effects; the baseline value of the response variable and the baseline HbA1c level as covariates; and a random effect for patient, with the FAS population.

The proportions of subjects achieving HbA1c target values (HbA1c <7.0% and ≤6.5%) at any point during the study (Weeks 6, 12, 18, 24, and 24-week endpoint [LOCF]) will be analyzed using Fisher's Exact test or Pearson's Chi-square test.

A listing of 7-point SMBG and 4-point SMBG will be presented for all the randomized subjects.

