5.2.11.5. Vital Signs

Vital signs measures (systolic blood pressure, diastolic blood pressure, and heart rate) and their change from baseline will be summarized by descriptive statistics (mean, median, SD, standard error, minimum, and maximum) by visit for the FAS population.

In addition, the MMRM model will evaluate the change from baseline in vital sign measure as the dependent variable with treatment (LY2963016, Lantus®), pre-study treatment (Lantus®-bolus, other basal-bolus, premixed insulin), and pre-study metformin or acarbose usage (metformin only, acarbose only, or neither), visit, and interaction between visit and treatment as fixed effects; the baseline value of the vital sign measure and the baseline HbA_{1c} level as covariates; and a random effect for patient. The LSMMeans will be estimated using the observed margins (OM) option in SAS MIXED procedure.

The number and percentage of patients with treatment-emergent outlier vital sign measures at each post baseline visit will be presented and analyzed using Fisher's exact test or Pearson's chi-square test for systolic blood pressure, diastolic blood pressure, and pulse rate according to the categories as listed below:

- low systolic blood pressure (≤ 90 mmHg and a decrease from baseline ≥ 20 mmHg)
- high systolic blood pressure (≥ 140 mmHg and an increase from baseline ≥ 20 mmHg)
- low diastolic blood pressure (≤ 50 mmHg and a decrease from baseline ≥ 10 mmHg)
- high diastolic blood pressure (≥ 90 mmHg and an increase from baseline ≥ 10 mmHg)
- low heart rate (< 50 bpm and a decrease from baseline ≥ 15 bpm)
- high heart rate (> 100 bpm and an increase from baseline ≥ 15 bpm)

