5.2.12. Subgroup Analyses

The consistency of the treatment effect for the change in HbA_{1c} level will be assessed in the following subgroups in the FAS population if there are sufficient numbers of patients in each treatment by subgroup (e.g. 20 patients per cell):

- Entry HbA_{1c} levels (<7%, ≥7%)
- Entry HbA_{1c} levels (<8.5%, ≥8.5%)
- Pre-study treatment (Lantus[®]-bolus, other basal-bolus, premixed insulin)
- Entry BMI (<30, ≥30)
- Entry BMI (<25, ≥25)
- Entry age (<65, ≥65)
- Entry age (<75, ≥75)
- Gender
- Prestudy metformin or acarbose use (metformin only, acarbose only or neither)
- Time of basal insulin injection (daytime, evening/bedtime)
- Renal function, as estimated by estimated glomerular filtration rate (EGFR) using the MDRD formula (see [Appendix 2](#)). The following EGFR categories will be used:

- normal or increased GFR: EGFR (≥ 90 mL/min/1.73 m²)
- mild reduction in GFR: EGFR (60 to 89 mL/min/1.73 m²)
- Moderate reduction in GFR: EGFR (30 to 59 mL/min/1.73 m²)
- Severe reduction in GFR: EGFR (15 to 29 mL/min/1.73 m²)
- Kidney failure: EGFR (< 15 mL/min/1.73 m²).

The categories severe reduction in GFR and kidney failure will be combined if there are fewer than 20 patients in either of these categories.

The change in HbA_{1c} from baseline to 24-week endpoint will be analyzed using MMRM with treatment, visit, prestudy treatment, prestudy metformin or acarbose usage, subgroup, subgroup-by-treatment interaction, subgroup-by-visit interaction, treatment-by-visit interaction, and treatment-by-visit-by-subgroup interaction as fixed-effects, the baseline value of HbA_{1c} as a covariate, and a random effect for patient for the FAS population. If the subgroup is one of the stratification variables, then the subgroup will only be included once in the model. A significant treatment-by-subgroup interaction ($p < .05$) may be indicative of a differential treatment effect across levels of the subgroup, necessitating further exploration of the nature of the interaction.

The contrast from the MMRM model with the OM option using PROC Mixed in SAS above will be used to obtain the LSmeans for change in HbA_{1c} levels from baseline to Week 24 within each treatment at each level of the subgroup. Additionally, the difference of these LSmeans between treatment groups with 95% confidence interval and p-values will be presented.

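### The primary MMRM names only a random patient effect, so the stated one-sided 2.5% at Week 24 depends on an unstated variance pattern over Weeks 6 to 24

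*SAP*

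**What the plan says.** SAP 5.2.7 and Protocol 12.2.6 define the primary analysis as a likelihood-based MMRM of change in HbA1c, fitted under missing at random. The model has treatment, pre-study treatment and pre-study metformin or acarbose use, followed by "visit, and interaction between visit and treatment as fixed effects; the baseline value of HbA1c as a covariate; and a random effect for patient". The SAP adds that SAS MIXED with observed margins will be used. I found no residual structure, visit-specific variance, convergence fallback, degrees-of-freedom method or robust standard error for this model in either document.

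The decision uses this model's own standard error: "The LSMean and standard error derived from the MMRM model for each treatment will be used to test noninferiority". Non-inferiority requires the upper 95% limit to lie below +0.4%. The reverse comparison requires the lower limit to lie above -0.4%. The SAP states that the sequence holds the family-wise error at one-sided 0.025.

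The covariance wording recurs for the secondary outcomes in SAP 5.2.8 ("the baseline value of the response variable and the baseline HbA1c level as covariates; and a random effect for patient"), for vital signs in SAP 5.2.11.5 ("level as covariates; and a random effect for patient") and for the HbA1c subgroup model in Protocol 12.2.10 ("the baseline value of HbA1c as a covariate, and a random effect for patient for the FAS") and SAP 5.2.12 ("as a covariate, and a random effect for patient for the FAS population"). The only variability figure is "a common standard deviation (SD) of 1.05% for change from baseline in HbA1c" in SAP 5.1.1.

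A supporting analysis is planned: "A second secondary analysis of the primary efficacy outcome will use an ANCOVA model with FAS population", with LOCF for missing Week 24 values.

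On a separate matter, Protocol 9.3 stratifies randomisation by screening HbA1c (below 8.5%, or 8.5% and above). The Protocol synopsis puts that stratum in the primary model; Protocol 12.2.6 and SAP 5.2.7 do not.

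**The concern.** A random patient effect with independent, equal residuals is compound symmetry with one variance for every visit. The treatment difference is tested at Week 24, but its standard error then borrows the variance of all four post-baseline HbA1c visits. If change from baseline varies less at the earlier visits than at Week 24, the interval is too narrow. If it varies more, the interval is too wide. If the average matches Week 24, the interval is right even when individual visits differ.

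Both non-inferiority conclusions, and the equivalence statement built on them, are read from this one interval. As written, its width depends on a programming choice and on a variance pattern that the documents do not describe.

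**Working it through.** **Inputs from the documents.** Margin 0.40%, SD 1.05%, true difference 0, one-sided alpha 0.025, power 80%, dropout 15% (SAP 5.1.1); post-baseline HbA1c at Weeks 6, 12, 18 and 24 (Protocol 7.2.2.4). SDs at Weeks 6, 12 and 18 and within-patient correlations are not given and are assumptions below.

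**The plan's own figure.** n per arm = 2 × (1.96 + 0.8416)² × 1.05² / 0.40² = 108.2, so 109; 109 / 0.85 = 128.2, so 129 per arm. Both figures reproduce.

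**Mechanism.** With complete data, the total variance estimated by the random-intercept model equals the mean of the visit variances. The Week 24 difference is therefore given variance 2 × mean(SD²)/n, while the true value is 2 × SD₂₄²/n. With r = √(mean(SD²)/SD₂₄²), the true one-sided error is Φ(-1.96 r). With dropout this is approximate.

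**Worked case, slight rise (0.90, 0.95, 1.00, 1.05).** Mean variance = (0.81 + 0.9025 + 1.00 + 1.1025)/4 = 0.95375. Divided by 1.1025 this is 0.865, so r = 0.930 and Φ(-1.823) = 3.4%. At 109 per arm the model SE is √(2 × 0.95375/109) = 0.132, against a true √(2 × 1.1025/109) = 0.142.

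**Simulation.** 10,000 trials per row at a true difference of +0.4: 258 patients randomised 1:1, random dropout of 5% after each of Weeks 6, 12 and 18, and constant correlation 0.6. Fixed effects were visit, treatment by visit and baseline. The random intercept used z = 1.96; the other two models used t with completers minus 3 degrees of freedom, as a stand-in for Kenward-Roger. Monte Carlo error is about ±0.3 points at 2.5%.

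| Assumed SDs, Weeks 6/12/18/24 | Formula | Random intercept | Unstructured | Heterogeneous CS |
|---|---|---|---|---|
| Flat, 1.05 throughout | 2.5% | 2.6% | 2.6% | 2.5% |
| Plateau, 1.00/1.05/1.05/1.05 | 2.6% | 2.6% | 2.4% | 2.4% |
| Unequal but balanced, 0.95/1.05/1.14/1.05 | 2.5% | 2.7% | 2.7% | 2.6% |
| Slight rise, 0.90/0.95/1.00/1.05 | 3.4% | 3.7% | 2.7% | 2.7% |
| Modest rise, 0.85/0.95/1.00/1.05 | 3.6% | 3.5% | 2.3% | 2.3% |
| Steady rise, 0.75/0.85/0.95/1.05 | 4.5% | 4.5% | 2.4% | 2.4% |

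The slight and modest rows are not distinguishable at this precision. A separate simulation with AR(1) correlation 0.8 gave the random intercept 2.5% for flat variance, and 3.3% (complete data) and 3.6% (15% dropout) for the slight rise. LOCF ANCOVA on the tabulated data stayed between 2.3% and 2.7%.

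**Tolerance.** Φ(-1.96 r) lies between 2.0% and 3.0% only for r between 0.96 and 1.05.

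**What the SAP's re-estimation model implies.** SAP 5.1.2.3 multiplies both the patient effect and the error by (1 - e^(-kt))/(1 - e^(-kd)). For every positive k this factor rises to 1 at study end, so r never exceeds 1. With k per week (an assumption, since no unit is given):

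| k | Mean variance / Week 24 variance | Formula error |
|---|---|---|
| 0.1 | 0.67 | 5.4% |
| 0.2 | 0.83 | 3.8% |
| 0.3 | 0.91 | 3.1% |
| 0.5 | 0.97 | 2.7% |
| 1 | 1.00 | 2.5% |

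The prior on k is uniform from 0.001 to 10 and described as non-informative. It fixes the direction, flat or rising, but not the size.

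**The case against.** The strongest reply is that this is incomplete specification and not a demonstrated error. The text calls the model an MMRM fitted in SAS MIXED and never says that residuals are independent or equal, so the sponsor may intend an unstructured matrix. That is possible. But a random patient effect is a different model from an unstructured matrix, and a programmer following the text would fit the former.

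Second, every SD before Week 24 is assumed. Protocol 7.2.1 and 9.4 expect most titration by Week 6, which would fit a plateau, and there the literal model is nominal. This stands, and it is why the figures are illustrative. It does not settle the matter, because the same sections allow titration up to Week 12 for some patients.

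Third, the LOCF ANCOVA does not pool visits and would expose a clearly wrong interval. That is true, but it is designated secondary, so the MMRM decides.

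Fourth, heterogeneous compound symmetry performed as well as unstructured, Kenward-Roger itself was not run, and the simulation omitted the pre-study treatment factors. This also stands: the results support visit-specific variances in general. Unstructured is the natural choice with four visits, not the only valid one.

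On the stratum, continuous baseline HbA1c is already a covariate, so little is likely to be gained by adding it. The point is the conflict between the synopsis and the detailed sections.

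**Conclusion.** The gap is real and should be closed. On the literal reading, the one-sided 2.5% claimed in SAP 5.2.7 is secured only if the average variance over Weeks 6 to 24 is close to the Week 24 variance, and nothing in the documents shows that it is. Illustratively, the error is about 2.5 to 2.7% for flat or early-plateau variance, 3.4 to 3.7% for a slight rise and 4.5% for a steady rise. These figures rest on assumed SDs and correlations and on random dropout. The variance that matters is the residual one after baseline and the other covariates, not the raw 1.05%. Under the SAP's own re-estimation model the literal fit is neutral or anti-conservative, by an amount that depends on k.

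Two stronger readings are not supported. A reader might infer that the trial's type I error is inflated, perhaps to about 6%. Simulation does give 6.0% for SDs of 0.52, 0.81, 0.96 and 1.05, but those are the re-estimation curve at k of about 0.1 per week, a rate the documents do not give. A reader might also infer a loss of power from variance that falls over time. An assumed fall from 1.20 to 1.05 gave 79.3% power against 83.4% with an unstructured matrix, but a falling pattern does not fit the SAP's own model for any k in its prior range.

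**What to change.** In Protocol 12.2.6 and SAP 5.2.7, replace the random patient effect with an unstructured within-patient covariance over Weeks 6, 12, 18 and 24, with Kenward-Roger degrees of freedom. Fix in advance a fallback order for non-convergence in which every step keeps visit-specific variances, for example heterogeneous Toeplitz and then heterogeneous compound symmetry. Use the same structure in the HbA1c subgroup model (Protocol 12.2.10, SAP 5.2.12). For the secondary and vital-sign models (SAP 5.2.8 and 5.2.11.5), name the same order and allow the fallback.

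This is a wording change before database lock. For HbA1c the covariance parameters rise from 2 to 4 × 5/2 = 10. If variance is flat, the power cost was 0.1 points in one run (82.5% against 82.4%) and 0.4 in another (83.7% against 83.3%). The fallback matters more elsewhere: six post-baseline visits for SMBG, weight and vital signs give 6 × 7/2 = 21 parameters, and eleven for insulin dose give 11 × 12/2 = 66.

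Separately, reconcile the Protocol synopsis with Protocol 12.2.6 and SAP 5.2.7 by including the screening HbA1c stratum, a randomisation factor, in the detailed models. This costs one parameter, and the expected gain is small.
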